6.9. Follow-up for patients who have permanently discontinued the study

If a subject discontinues participation in the study, he or she will be contacted to obtain information about the reason(s) for discontinuation and collection of any potential Aes. The Investigator will document the reason for Subject Withdrawal on the Patient Case Report Form (CRF). Discontinued patients will be followed until all Aes resolve or until the Investigator decides that follow-up are no longer needed.

7. Patient selection

EndoscoPic Submucosal Dissection using gel versus glycerol for submucosal injection: a randomized controlled multicentric trial (EPSILON)

Version 1 – dated 21/07/2021

7.1. Inclusion criteria

- Subject ≥18 years of age at the time of informed consent
- Patients must have given written informed consent
- Subjects with documented gastric or rectal lesions with indication of endoscopic removal by ESD, namely:
 - Gastric focal lesion with suspicion of early gastric cancer (low or high grade dysplasia with features of early gastric cancer; adenocarcinoma with morphology of superficial lesion and work-up of superficial lesion)
 - Rectal polyps (adenoma or superficial carcinoma) from 0 to 15 cm from the anal margin; with features being recognized indications of ESD: more than 20mm granular LST, more than 20mm non granular LST, more than 20mm villous or bulging polyps, Paris 0-IIa+IIc lesions, lesions with suspicious pattern (Kudo Vi / JNET 2B), lesions with anal canal involvement.

7.2. Exclusion criteria

- Subjects who meet any of the following exclusion criteria cannot be enrolled in the study:
 - Gastric and rectal neuroendocrine tumour (NET) with indication of ESD will be excluded
 - Gastric and rectal lesions with indication of ESD but strong fibrosis due to previous partial resection will be excluded
 - Subject is currently enrolled in another confounding research
 - Subjects with any other location of ESD (esophagus, duodenum and colon) will not be included.

8. Study procedure

8.1. Screening endoscopy

Patients will be addressed for ESD by their gastroenterologist after index gastroscopy/colonoscopy showing a potential superficial (pre)neoplastic lesion. A “second look” endoscopy before being admitted for ESD remains at the discretion of the endoscopist. Further investigations by EUS, pelvic MRI or/and chest and abdominal CT scan will be recommended depending on the endoscopic evaluation and center oncological consensus management.

8.2. ESD procedure

First, the lesion will be closely inspected by high-resolution endoscopy with white light and narrow banding imaging (NBI) with near focus (GIF-HQ190 Olympus Medical System, Tokyo, Japan). Size, shape (Paris classification, LST classification for rectum), endoscopic features (NICE and JNET classification) and location will be reported¹¹⁻¹³.

The ESD procedures will be performed under general anesthesia with orotracheal intubation or under sedation following center experience. Carbon dioxide will be used for insufflation.

Using an HQ 190 Olympus gastroscope (EXERA III) or 290 series (LUCERA) in Japan or 1500EZ using Evis X1), fitted with a transparent cap at its end (D-206 or equivalent; Olympus), the gastric lesions will be delimited and marked by the ESD knife tip (i.e Dual-(J) Knife (Olympus Medical Systems, Tokyo, Japan), with soft coagulation mode (VIO 300 Effect 5, 50 watts; VIO3 E 5.5). Marking dots are not required for rectal lesions due to their clear delineation from the normal mucosa.

According to randomization, using a 25G needle, the lesion will be lifted with a Glyceol solution with indigo blue dye or ORISE™ gel. Mucosal incision will be performed using Dry Cut mode, (E3 30 watts Erbe VIO 300D, E 3.5 Erbe VIO 3; Tubingen, Germany) and subsequent submucosal dissection using dry cut or swift coagulation mode, (VIO 300 E4 30watts; VIO3 E3.5). After mucosal opening, further lifting during the ESD will be performed using the needle or the tip of the knife pushed into the submucosal space with the Glyceol or ORISE™ gel according to randomization. Added saline injected through the tip of the knife is allowed in both groups (with recorded volume) according to the endoscopists convenience. Visible vessels and bleedings will be coagulated with the knife tip (slowly using swift coag E4 30W or using Forced coag E1 15W) or a 4mm (rectum) or 5mm (stomach) coagulation forceps (Coagrasper, Olympus), using soft coagulation (VIO 300 Effect 5, 50 watts (rectum) / 80 watts (stomach); VIO3 E 5.5). For gastric ESD, 80mg of Intravenous PPI will be given during the procedure and 12h later; at discharge PPI 40mg BID will be given after gastric ESD. After the resection, the specimen will be pinned on a cork (or equivalent) to stretch it moderately and expose the lateral margins. Then, measures of the maximal diameter (mm) and perpendicular minimal diameter will be obtained and recorded by picture capture using the scope. Thereafter, it will be immersed into formaldehyde and sent to the pathologic lab.

Patients will remain hospitalized overnight and a blood test will be performed before their discharge.

9. Assessments per procedure

- Duration of ESD procedure defined as the time of first injection to final cut time
- Total duration of the endoscopic procedure (from endoscope insertion to scope retrieval)
- Calculated speed of the dissection (surface dissected (mm²)/ESD duration (min)).
- Number of per-procedural bleeding (+ severity scale: oozing / severe non pulsating/ severe pulsating)
- Total hemostatic time (addition of each hemostasis time for each per-procedural bleeding)
- Need for haemostatic forceps during ESD
- Difficulty of the dissection (scale)
- Amount of submucosal solution (glycerol or gel) used for ESD in ml

EndoscoPic Submucosal Dissection using gel versus glycerol for submucosal injection: a randomized controlled multicentric trial (EPSILON)

Version 1 – dated 21/07/2021

- Combined use of saline through the knife during ESD (number and ml)
- Number of needle injection dots during ESD (initially / during ESD)
- Need to adjust electrosurgical settings during ESD
- Clear visualisation of the plane of dissection during ESD (scale)
- Rate of en-bloc dissection
- Rate of endoscopic complete resection
- Quality assessment of the pathological specimen
- Adverse events:
 - Per-procedural (incidence of all adverse technical events during the procedure)

10. Adverse event

10.1. Reporting of adverse events (AE), serious adverse events (SAE), serious adverse device effects (SADE), unanticipated serious adverse device effects (USADE)

All adverse events (AE), serious adverse events (SAE), Serious Adverse Device Effects (SADE), Unanticipated serious adverse device effects (USADE) will be collected and documented in the source documents and appropriate case report forms (CRF) during the entire study period, i.e. from patient's informed consent until the last protocol-specific procedure, including a safety follow-up period. Documentation includes dates of event, treatment, resolution, assessment of seriousness and causal relationship to device and/or study procedure.

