5.2. Study endpoints

5.2.1. Primary

- Increase the dissection speed of the ESD procedure (defined as the dissected surface (mm²)/ESD duration (min)). The dissected surface is defined as maximal diameter of specimen (mm) x perpendicular minimal diameter of specimen (mm) measured on ex-vivo pinned stretched specimen onto a cork. ESD duration is defined as the time from first submucosal injection to final cut time.

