5.2.2. Secondary

- Total procedure duration (from scope insertion to scope retrieval) (min)
- Number of per-procedural bleeding (+ severity scale: oozing / severe non pulsating/ severe pulsating)
- Total hemostatic time (addition of each hemostasis time for each per-procedural bleeding)

EndoscoPic Submucosal Dissection using gel versus glycerol for submucosal injection: a randomized controlled multicentric trial (EPSILON)

Version 1 – dated 21/07/2021

- Need for haemostatic forceps during ESD
- Difficulty of the dissection (scale)
- Amount of submucosal solution (glycerol or gel) used for ESD in ml
- Combined use of saline through the knife during ESD (number and ml)
- Number of needle injection dots during ESD (initially / during ESD)
- Need to adjust electrosurgical settings during ESD
- Clear visualisation of the plane of dissection during ESD (scale). The scale will be defined according the endoscopists evaluation of the delineation between the submucosa ad the underlying muscular layer:
 - Very-good visualization: clear delineation between the two layers with clear visualization of the blood vessels.
 - Good visualization: mostly clear delineation between the two layers, but with blurred regions
 - Bad visualization: delineation between the two layers is unclear (i.e.: fibrosis)
- Rate of en-bloc dissection (defined as endoscopic resection of the targeted area in one bloc)
- Rate of complete endoscopic resection (defined as endoscopic evaluation of complete removal of the targeted area in the treated organ)
- Quality assessment of the pathological specimen (absolute measure of the depth of resected submucosa on the specimen, rate of clear (horizontal and vertical) margins)
- Adverse events:
 - Per-procedural (incidence of all adverse technical events during the procedure)
 - Early (clinical and laboratory at 24 h post procedure according to CTCAE v 5.0)
 - Late (clinical at 2-3 weeks follow-up)

6. Study design

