6.1. Study design

We aim to conduct an multicentric, open label, prospective randomized (1 :1) academic study comparing the submucosal injection using ORISE™ gel and glycerol in a specific population with superficial GI (pre)neoplastic lesions (see Schedule of assessments in Table 1). Patients will be referred by their gastroenterologist after index gastroscopy/colonoscopy showing a potential superficial (pre)neoplastic lesion.

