3 ENDPOINT ANALYSIS

3.1 Primary Endpoint

Increase the dissection speed of the ESD procedure (defined as the dissected surface (mm²)/ESD duration (min)). The dissected surface is defined as maximal diameter of specimen (mm) x perpendicular minimal diameter of specimen (mm) measured on ex-vivo pinned stretched specimen onto a cork. ESD duration is defined as the time from first submucosal injection to final cut time.

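### The area in the primary endpoint is measured unmasked on a specimen stretched to a discretionary tension, and no masked check of it, or of the pathology readings, is planned

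*Protocol*

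**What the plan says.** Protocol section 6.1 describes the design: "We aim to conduct an multicentric, open label, prospective randomized (1 :1) academic study". Section 5.2.1 defines the primary endpoint as dissected area over ESD duration. The area is the largest diameter times the diameter perpendicular to it, and the clock runs from the first injection to the last cut. SAP section 3.1 repeats the definition, with the diameters "measured on ex-vivo pinned stretched specimen onto a cork".

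Protocol section 8.2 gives the method. Once the resection is finished, "the specimen will be pinned on a cork (or equivalent) to stretch it moderately and expose the lateral margins". The section does not say who does the pinning and gives no tension standard beyond moderate. On how size is taken, it states that "measures of the maximal diameter (mm) and perpendicular minimal diameter will be obtained and recorded by picture capture using the scope". It does not name the measurer or ask for a scale in the picture. Fixation and dispatch to the pathology laboratory come after that.

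Pathology has its own secondary endpoint in section 5.2.2: "Quality assessment of the pathological specimen (absolute measure of the depth of resected submucosa on the specimen, rate of clear (horizontal and vertical) margins". Neither document says that these readings, or the two diameters, are made without knowledge of the arm. SAP section 3.1 contains no sensitivity analysis for the measured area.

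**The concern.** The operator handles the two solutions and cannot be blinded. The usual protection is then to have what can be measured masked measured that way. Here the numerator of the primary endpoint is a reading that leaves room for judgement, in how far the tissue is stretched and where the diameters are taken. It is made while the specimen is still with the endoscopy team. The protocol states a directional hypothesis in the synopsis and a favourable preliminary experience with gel in section 4.

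A proportional error in each diameter enters the area squared. If gel specimens were read slightly larger than glycerol specimens, part of any observed gain in speed would be measurement, and the plan contains nothing that would show it. Submucosal depth and margin status are exposed in the same way if the pathologist knows the solution, although they could easily be read masked.

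**Working it through.** **Inputs.** From the table in Protocol section 6.2 and SAP section 3.1.1: glycerol 17.11 ± 18.27 mm²/min, gel 22.24 ± 10.26, difference 5.13; two-sided Welch test, alpha 0.05, power 80%, 133 per arm. The between-arm difference per diameter, *s*, is not in the documents and is assumed.

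**The plan's own figure.** SE = √((18.27² + 10.26²)/133) = √(439.06/133) = 1.817. Welch power from the noncentral t with Satterthwaite degrees of freedom is 79.9% at 132 per arm and 80.2% at 133. The planned 133 per arm reproduces.

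**Spurious difference.** Let both true means be 17.11, and let each gel diameter read larger by a fraction *s*. The gel area is multiplied by (1+*s*)², so the spurious difference is 17.11 × ((1+*s*)² − 1).

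- *s* = 3%: 17.11 × 0.0609 = 1.04, and 1.04/5.13 = 20%
- *s* = 5%: 17.11 × 0.1025 = 1.75, and 1.75/5.13 = 34%
- *s* = 10%: 17.11 × 0.2100 = 3.59, and 3.59/5.13 = 70%

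**What it takes to create the planned effect.** Half of it needs √(1 + 2.565/17.11) − 1 = 7.2% per diameter. All of it needs √(22.24/17.11) − 1 = 14.0%. On an assumed 30 mm diameter, 5% is 1.5 mm and 14% is 4.2 mm.

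**Chance of a significant result with no true effect, 133 per arm.** Multiplying every gel area by (1+*s*)² also multiplies the gel SD. At 10% the gel SD becomes 10.26 × 1.21 = 12.41 and the SE √((18.27² + 12.41²)/133) = 1.915. The table gives the rejection rate with that scaling (Welch), without it (normal approximation, SE 1.817), and with both SDs at 18.27 before scaling (Welch).

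| *s* per diameter | planning SDs, gel SD scaled | planning SDs, not scaled | both SDs 18.27, gel SD scaled |
|---|---|---|---|
| 3% | 8.7% | 8.8% | 7.3% |
| 5% | 15.5% | 16.2% | 11.5% |
| 10% | 46.4% | 50.7% | 30.2% |

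The smallest observed difference that reaches significance is about 1.97 × 1.817 = 3.58 mm²/min, which a difference of about 10% per diameter produces by itself.

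**The case against.** A reader might infer that the area is measured during the dissection by the operator. The documents do not say so. The measurement follows the resection, is made ex vivo, falls after the ESD clock has stopped, and has no named measurer. That the measurer knows the arm is a strong inference, not a stated fact.

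A reader might also infer that slight stretching could account for most of the planned effect. The figures do not support that: 1% to 3% per diameter gives 7% to 20% of it, and half needs about 7%, systematically and in both diameters. Only a consistent difference between arms biases the comparison. Stretch that varies alike in both arms adds noise, and randomization stratified by center and organ balances local pinning habits.

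Three further points stand in part.

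- The pictures already required could be re-read masked, so a positive result is not beyond checking for reading error. But no such reading is planned and no scale is required in the picture.
- A pathologist who measures the pinned specimen inherits whatever stretch was applied, so masking there removes reading bias and nothing else.
- Start and stop times are also recorded unmasked, and the stated hypothesis concerns duration. The numerator is therefore only half of the exposure. The times are at least tied to two discrete events, whereas the degree of stretch is left open.

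Finally, no pathology request form is described. The documents do not show that allocation is disclosed to the pathologist, only that nothing prevents it.

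**Conclusion.** The point holds as a missing and inexpensive safeguard. Followed exactly, the plan leaves a discretionary, unmasked reading in the numerator of its primary endpoint, with no masked check of it and no masking of the depth and margin readings. Differences of 5% per diameter would be worth about a third of the planned effect and would raise the false-positive rate from 5% to between about 12% and 16%, depending on the SDs. At 10% the rate is about 30% to 51%. These sizes rest on assumed values of *s*, on no true effect, and on the pilot means and SDs. The documents contain nothing on how much stretch or reading varies.

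It would go too far to conclude that such a bias is present, or that a positive result would be uninterpretable. The documents support only that the plan could neither exclude nor detect the bias. The matter should be corrected, but it does not invalidate the design, the primary definition or the sample size.

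**What to change.** 1. **Protocol 8.2, pathology.** Send the specimen under its study code with the injected solution left off the request, and state that submucosal depth and margins are read without knowledge of the arm.
2. **Protocol 8.2, pinning.** Write one pinning instruction that applies identically in both arms, name the role that measures, and require a ruler in the picture that is already captured.
3. **Pathology CRF and SAP 3.1.** Have the pathologist who already examines the specimen record the same two diameters masked to arm. Add a supportive analysis that repeats the primary comparison of dissection speed with these diameters and the same ESD durations. If fixation shrinks specimens by the same factor in both arms, both speeds are rescaled alike and the Welch statistic does not change. The two analyses should therefore be compared on the relative difference, not in mm²/min.

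**Cost.** One line on the request, a ruler, two numbers on the pathology CRF and one repeated analysis. No extra staff, procedure or patients.

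**Limits to state in the SAP.** The analysis checks reading bias only. It does not remove differential stretch applied at pinning, or bias in the unmasked start and stop times. Fixation may change specimen size, not necessarily equally in the two arms. Masking may be incomplete if gel can be recognised in the tissue.

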10.2. Definition and assessment of (serious) adverse events and other safety related events

10.2.1. Adverse Event (AE)

Any untoward medical occurrence, unintended disease or injury or any untoward clinical signs (including an abnormal laboratory finding) in subjects, users or other persons whether or not related to the investigational medical device.

NOTE 1: This definition includes events related to the investigational device or the comparator. NOTE 2: This definition includes events related to the procedures involved.

NOTE 3: For users or other persons, this definition is restricted to events related to investigational medical device.

10.2.2. Serious Adverse Event (SAE)

Adverse event that:

EndoscoPic Submucosal Dissection using gel versus glycerol for submucosal injection: a randomized controlled multicentric trial (EPSILON)

Version 1 – dated 21/07/2021

- a) led to a death, injury or permanent impairment to a body structure or a body function.
- b) led to a serious deterioration in health of the subject, that either resulted in:
 - a life-threatening illness or injury, or
 - a permanent impairment of a body structure or a body function, or- in-patient hospitalization or prolongation of existing hospitalization, or- in medical or surgical intervention to prevent life threatening illness.
- c) led to foetal distress, foetal death or a congenital abnormality or birth defect.

NOTE 1: Planned hospitalization for pre-existing condition, or a procedure required by the Clinical Investigation Plan, without a serious deterioration in health, is not considered a serious adverse event.

10.2.3. Device deficiency

Inadequacy of an investigational medical device related to its identity, quality, durability, reliability, safety or performance. This may include malfunctions, use error, or inadequacy in the information supplied by the manufacturer.

10.2.4. Adverse Device Effect (ADE)

Adverse event related to the use of an investigational medical device.

NOTE 1- This includes any adverse event resulting from insufficiencies or inadequacies in the instructions for use, the deployment, the implantation, the installation, the operation, or any malfunction of the investigational medical device.

NOTE 2- This includes any event that is a result of a use error or intentional abnormal use of the investigational medical device.

10.2.5. Serious Adverse Device Effect (SADE)

Adverse device effect that has resulted in any of the consequences characteristic of a serious adverse event.

10.2.6. Unanticipated Serious Adverse Device Effect (USADE)

Serious adverse device effect which by its nature, incidence, severity or outcome has not been identified in the current version of the risk analysis report.

NOTE: Anticipated SADE (ASADE): an effect which by its nature, incidence, severity or outcome has been previously identified in the risk analysis report.

10.3. Causality assessment

The relationship between the use of the medical device 13 (including the medical - surgical procedure) and the occurrence of each adverse event shall be assessed and categorized. During causality assessment activity, clinical judgement shall be used and the relevant

EndoscoPic Submucosal Dissection using gel versus glycerol for submucosal injection: a randomized controlled multicentric trial (EPSILON)

Version 1 – dated 21/07/2021

documents, such as the Investigator's Brochure, the Clinical Protocol or the risk Analysis Report shall be consulted, as all the foreseeable serious adverse events and the potential risks are listed and assessed there. The presence of confounding factors, such as concomitant medication/treatment, the natural history of the underlying disease, other concurrent illness or risk factors shall also be considered. The above considerations apply also to the serious adverse events occurring in the comparison group. For the purpose of harmonising reports, each SAE will be classified according to five different levels of causality. The sponsor and the investigators will use the following definitions to assess the relationship of the serious adverse event to the investigational medical device or procedures.

1. Not related: relationship to the device or procedures can be excluded when:
 - ✓ the event is not a known side effect of the product category the device belongs to or of similar devices and procedures;
 - ✓ the event has no temporal relationship with the use of the investigational device or the procedures;
 - ✓ the serious event does not follow a known response pattern to the medical device (if the response pattern is previously known) and is biologically implausible;
 - ✓ the discontinuation of medical device application or the reduction of the level of activation/exposure - when clinically feasible - and reintroduction of its use (or increase of the level of activation/exposure), do not impact on the serious event;
 - ✓ the event involves a body-site or an organ not expected to be affected by the device or procedure;
 - ✓ the serious event can be attributed to another cause (e.g. an underlying or concurrent illness/ clinical condition, an effect of another device, drug, treatment or other risk factors);
 - ✓ the event does not depend on a false result given by the investigational device used for diagnosis, when applicable;
 - ✓ harms to the subject are not clearly due to use error;
 - ✓ In order to establish the non-relatedness, not all the criteria listed above might be met at the same time, depending on the type of device/procedures and the serious event.
2. Unlikely: the relationship with the use of the device seems not relevant and/or the event can be reasonably explained by another cause, but additional information may be obtained.
3. Possible: the relationship with the use of the investigational device is weak but cannot be ruled out completely. Alternative causes are also possible (e.g. an underlying or concurrent illness/ clinical condition or/and an effect of another device, drug or treatment). Cases where relatedness cannot be assessed or no information has been obtained should also be classified as possible.
4. Probable: the relationship with the use of the investigational device seems relevant and/or the event cannot reasonably explained by another cause, but additional information may be obtained.
5. Causal relationship: the serious event is associated with the investigational device or

EndoscoPic Submucosal Dissection using gel versus glycerol for submucosal injection: a randomized controlled multicentric trial (EPSILON)

Version 1 – dated 21/07/2021

with procedures beyond reasonable doubt when:

- ✓ the event is a known side effect of the product category the device belongs to or of similar
- ✓ devices and procedures;
- ✓ the event has a temporal relationship with investigational device use/application or procedures;
- ✓ the event involves a body-site or organ that
 - o the investigational device or procedures are applied to;
 - o the investigational device or procedures have an effect on;
- ✓ the serious event follows a known response pattern to the medical device (if the response pattern is previously known);
- ✓ the discontinuation of medical device application (or reduction of the level of activation/exposure) and reintroduction of its use (or increase of the level of activation/exposure), impact on the serious event (when clinically feasible);
- ✓ other possible causes (e.g. an underlying or concurrent illness/ clinical condition or/and an effect of another device, drug or treatment) have been adequately ruled out;
- ✓ harm to the subject is due to error in use;
- ✓ the event depends on a false result given by the investigational device used for diagnosis when applicable;
- ✓ In order to establish the relatedness, not all the criteria listed above might be met at the same time, depending on the type of device/procedures and the serious event

The following events will be reported by the sponsor-investigator to the Competent Authorities ([contact]):

- any SAE
- any Device Deficiency that might have led to a SAE if:
 - ✓ suitable action had not been taken or
 - ✓ intervention had not been made or
 - ✓ if circumstances had been less fortunate
- any new findings/updates in relation to already reported events.

by using the European Form:

https://www.fagg-afmps.be/sites/default/files/downloads/sae_reporting_form_en.xlsx

